1.4.2. Description of Etoposide

Etoposide is a cytotoxic chemotherapy and is classified as a topoisomerase II enzyme inhibitor. It is administered intravenously and is indicated in combination with other chemotherapeutic agents for the treatment of AML.

1.4.3. Description of Cytarabine

Cytarabine is a cytotoxic chemotherapy and an antimetabolic agent. It is administered intravenously and is indicated as a single agent or in combination with other chemotherapeutic agents for the treatment of AML.

1.4.4. Clinical Data for Mitoxantrone, Etoposide, and Cytarabine

MEC is considered a long-standing SOC option for AML patients who are relapsed after or refractory to initial induction chemotherapy. Multiple clinical studies have evaluated MEC in the R/R setting and have demonstrated clinical activity, with a CR rate of approximately 20% and a median OS of approximately 3 to 5 months {Greenberg 2004, Roboz 2014}. MEC has a similar safety profile to other salvage chemotherapy regimens used in AML, most notably myelosuppression.

1.5. Information About CC-486

1.5.1. Description of CC-486

CC-486 (Onureg) is an oral HMA indicated for continued treatment of adult patients with AML who achieved first CR or CRi following intensive chemotherapy and who are not able to complete curative therapy {ONUREG 2020}. CC-486 is given orally on a daily dosing regimen.

1.5.2. Clinical Data for CC-486

CC-486 was approved by the US FDA in 2020 for the treatment of AML patients in CR or CRi following intensive chemotherapy. This approval was supported by data from the randomized Phase 3 QUAZAR study comparing CC-486 versus placebo in patients 55 years and older who were in first CR or CRi following intensive chemotherapy and/or consolidation and were ineligible for hematopoietic SCT. The median OS was significantly longer for patients who received CC-486 than for those who received placebo (24.7 vs. 14.8 months, HR 0.69). Relapse-free survival was also significantly longer for patients who received CC-486 than those who received placebo (10.2 vs. 4.8 months) {Abrisqueta 2019}. The MRD negative response rate for CC-486 (CR/CRi MRD positive to CR/CRi MRD negative) was 37%, although a high degree of MRD negativity conversion was also observed in the placebo arm (19%) {Roboz 2020}. In summary, CC-486 has emerged as a SOC option for maintenance therapy in AML patients in first remission who are not candidates for SCT.

1.6. Rationale for This Study

Patients with either newly diagnosed AML who are unfit for intensive chemotherapy or have R/R AML or MRD positive disease require improvements in clinical outcomes. Outside of an allogeneic SCT, there are limited curative therapies available for these patients. Thus, novel treatments that have a strong scientific and clinical rationale are needed to improve clinical outcomes. Magrolimab is being evaluated in each of these patient populations based on the strong scientific rationale for the proposed magrolimab combinations and clinical data supporting these evaluations.

[figure not shown]
Cohort 1 was closed to enrollment given that sufficient safety and efficacy data have been attained from Study 2020-0027 at MD Anderson Cancer Center (MDACC) to support further testing of the Mag+Ven+Aza combination in the currently active Phase 3 Study GS-US-590-6154 (ENHANCE-3).

Cohort 3 was closed to enrollment due to lack of enrollment.

1.6.1. Cohort 1 (1L Unfit AML Mag+Ven+Aza): Magrolimab in Combination with Azacitidine and Venetoclax in Patients with Newly Diagnosed, Previously Untreated AML Who Are Ineligible for Intensive Chemotherapy

Magrolimab is under clinical evaluation in combination with azacitidine in the ongoing Phase 1b study, 5F9005, in patients with AML who are previously untreated and ineligible for intensive induction chemotherapy. Among 34 evaluable patients, 65% achieved an OR and 44% achieved a CR. Time to response was rapid (median 2.04 months) {Sallman 2020a}. Clinical activity has also been observed in patients with the *TP53* mutation, a poor-risk subgroup with an overall response rate (ORR) of 71%. Median OS was 12.9 months in patients with the *TP53* mutation and 18.9 months in patients with wild-type *TP53*. Given the encouraging efficacy data observed with the magrolimab plus azacitidine and venetoclax plus azacitidine double combinations, the triple combination of magrolimab plus azacitidine plus venetoclax is anticipated to show superior activity over either double combination. Furthermore, nonclinical data demonstrate that venetoclax can enhance magrolimab-mediated phagocytosis, which can be further enhanced by azacitidine (Figure 3).

Figure 3. In Vitro Phagocytosis of AML Cells with Magrolimab, Azacitidine and/or Venetoclax

AML = acute myeloid leukemia

Human macrophages were incubated with AML HL60 cells in the presence of the indicated therapeutic agents with macrophage phagocytosis of AML cells measured.

Based on the nonclinical and clinical data described here, an investigator-initiated study sponsored by the MDACC commenced in the second half of 2020 to evaluate the safety, tolerability, recommended dose, and preliminary efficacy of magrolimab plus azacitidine and venetoclax in R/R AML patients and frontline AML patients who are ineligible for intensive chemotherapy. Emerging data from that study have informed design elements for this study. Venetoclax and azacitidine have overlapping toxicities, particularly myelosuppression and infections. Anemia, neutropenia, thrombocytopenia, and infections have been reported in patients treated with magrolimab.

In summary, the nonclinical rationale and clinical data support the evaluation of magrolimab in combination with azacitidine and venetoclax in frontline AML patients who are ineligible for intensive chemotherapy.

1.6.2. Cohort 2 (R/R AML Mag+MEC): Magrolimab in Combination with MEC in Patients with AML Who Are Refractory to or Have Relapsed After Initial Induction Chemotherapy

Patients with primary refractory AML or in relapse from AML after induction chemotherapy have a poor prognosis and a median OS of less than 6 months despite receiving SOC therapy with salvage chemotherapy. MEC is a commonly used salvage chemotherapy option in this setting but yields CR rate of approximately 20% and a median OS of approximately 5 months {Greenberg 2004, Roboz 2014}. Thus, combination therapies that can enhance the efficacy of MEC are needed to improve clinical outcomes. Cytotoxic chemotherapies can synergize with magrolimab, which increases prophagocytic signals on tumor cells by blocking the antiphagocytic CD47 signal, thus enhancing phagocytosis. Nonclinical data have demonstrated both in vitro and in vivo that the antitumor activity of magrolimab is enhanced when combined with chemotherapy ({Sikic 2016} and data on file). The combination of mitoxantrone and etoposide (components of MEC chemotherapy) induces high rates of prophagocytic signal expression (specifically calreticulin) and macrophage phagocytosis compared with other chemotherapeutic agents {Obeid 2007}. Given these nonclinical proof-of-concept data and the common usage of MEC as a salvage chemotherapy in R/R AML, the combination of magrolimab with MEC is under evaluation in this study.

1.6.3. Cohort 3 (Post-Chemo Maint Mag+CC-486): Magrolimab in Combination with CC-486 in Patients with AML who Achieve CR or CRi with MRD Positivity after Intensive Induction Chemotherapy

As described above, AML patients who achieve a CR or CRi after induction chemotherapy or consolidation therapy, particularly those who are MRD positive, have a significant risk of relapse prior to starting maintenance therapy. CC-486 is a SOC option for older patients after induction chemotherapy who are ineligible for SCT. Despite the clinical benefit observed, OS and RFS were approximately 14.6 months and 7.1 months for patients who were MRD positive and treated with CC-486 {Roboz 2020}. Thus, novel agents that can be safely combined with CC-486 to extend RFS are needed. Strong nonclinical and clinical rationale exists for treatment of this population with the combination of magrolimab and CC-486. CC-486 is an oral therapy with similarities to azacitidine. Magrolimab, which acts by blocking anti-phagocytic CD47, has been shown in vitro and in vivo to synergize with azacitidine, which upregulates prophagocytic signals on leukemic cells, thus leading to enhanced phagocytosis (Feng 2018). Clinically, magrolimab enhances azacitidine activity in patients with untreated AML who are unfit to receive intensive chemotherapy. Magrolimab + azacitidine led to a 65% ORR with a 44% CR rate in an ongoing Phase 1b study in this population {Sallman 2020a}. These results compare favorably with historical azacitidine CR rates, which are approximately 10% to 20%. Notably, 37% of patients with CR/CRi achieved MRD negativity, an important outcome measure in this maintenance AML cohort. In addition, the safety profile of magrolimab + azacitidine was well tolerated, with no MTD reached and only 3.8% of patients discontinuing therapy due to a treatment-related AE. Based on these clinical data, the combination of magrolimab with CC-486 is anticipated to be well tolerated and efficacious and lead to higher rates of MRD negativity and RFS, key outcomes for this population.

1.7. Rationale for Dose Selection of Magrolimab

The rationale for the magrolimab dose proposed in this study originates from safety, efficacy, and PK/pharmacodynamics (PD) data, and modelling and simulation analyses based on data obtained from all ongoing and completed clinical studies with magrolimab in patients with solid tumors, NHL, and AML/MDS.

In the first-in-human study of magrolimab (SCI-CD47-001) in patients with solid tumors and lymphomas, after an initial priming dose of 1 mg/kg on the first day, magrolimab was tested as a monotherapy at weekly doses of up to 45 mg/kg. The use of an initial 1 mg/kg priming dose was integrated into the dosing regimen to mitigate the on-target anemia induced by CD47 blockade. An initial priming dose leads to elimination of aged RBCs that are sensitive to CD47 blockade and triggers reticulocytosis of young RBCs that are not affected by CD47 blockade {Chen 2018}. Utilizing a priming dose leads to an initial, transient, and mild anemia that generally normalizes back to baseline over several weeks, even in the presence of repeated therapeutic doses of magrolimab {Advani 2018, Liu 2015a, Sikic 2019}. The maximum weekly dose of 45 mg/kg has an acceptable safety profile, and no MTD was identified in this study.

In Studies SCI-CD47-002 and 5F9005 in patients with AML/MDS, magrolimab was administered as a monotherapy at doses of up to 30 mg/kg twice weekly and in combination with azacitidine at doses of up to 30 mg/kg once weekly. In these studies, no significant dose-limiting toxicity (DLT) was observed, and magrolimab had an acceptable safety profile over the tested dose range up to a maximum of 30 mg/kg twice weekly. In transfusion-dependent lower-risk MDS patients (Study 5F9005), a magrolimab dosing regimen of 60 mg/kg is being evaluated. This dose was shown to be safe and well tolerated in the initial DLT evaluation period, with no DLTs observed as of October 2020. Furthermore, in these 2 studies, an intrapatient dose escalation approach was followed; after the priming dose, the patients received doses of 15 mg/kg on Day 8 during Week 2, after which the dose was escalated to 30 mg/kg on Day 11 and then weekly thereafter. This schedule was based on nonclinical data indicating enhanced safety of intrapatient dose escalation. In studies 5F9003 and 5F9004, magrolimab, in combination with rituximab and cetuximab, respectively, was found to have an acceptable safety profile at doses up to 45 mg/kg every week followed by every other week.

The proposed dosing regimen of magrolimab in this study is expected to have an acceptable safety profile based on the entirety of safety data in multiple oncology populations including the proposed study population, both as a monotherapy and in combination with other tumor-targeted antibodies and chemotherapeutics.

In Study SCI-CD47-002 and Study 5F9005, CD47 RO by magrolimab was tested at baseline and at multiple time points on treatment, on both peripheral blood and bone marrow cells, including leukemic blasts. A PK/PD model linking dose exposure and blood and bone marrow RO was developed and described these data well. Simulations with the model predicted that > 90% RO would be achieved in the bone marrow cells at the magrolimab dosing regimens proposed in this study. This level of RO is typically associated with maximal efficacy for all immune-oncology antibodies. Therefore, the proposed dose regimens are expected to maximize efficacy in the AML patient populations.

Based on results from the Phase 1b study of magrolimab in MDS and AML (Study 5F9005), the current study is designed to employ the same intrapatient dose escalation regimen for magrolimab to mitigate on-target toxicities such as anemia and other toxicities observed in nonclinical AML models. Treatment should be continued until disease progression, relapse, loss of clinical benefit, or unacceptable toxicity occur.

In summary, the proposed dose regimens have been shown to have acceptable safety profiles in oncology patient populations. Based on PK/PD modeling, the proposed doses are predicted to result in optimal efficacy in myeloid malignancy populations and maximize patient and caregiver convenience.

1.8. Risk/Benefit Assessment for the Study

For each of the study cohorts, strong scientific, nonclinical, and clinical data exist that support the rationale to evaluate magnolimab combinations in the selected patient populations.

For the 1L Unfit AML Mag+Ven+Aza cohort (Cohort 1), nonclinical data demonstrate enhanced efficacy when magrolimab is combined with venetoclax and azacitidine. Furthermore, encouraging clinical activity is observed with both the magrolimab plus azacitidine and venetoclax plus azacitidine double combinations, supporting the concept that a triple combination may lead to improved efficacy. Venetoclax and azacitidine have overlapping toxicities, particularly myelosuppression. Anemia, neutropenia, thrombocytopenia, and infections have also been reported in patients treated with magrolimab, and management guidelines for these risks provided in Section 7.8.1. The combination of Mag+Ven+Aza is anticipated to be well tolerated. Specific mitigation measures, including an inclusion criterion requiring $Hb \geq 9$ g/dL at the initiation of study treatment, magrolimab priming/maintenance dosing regimen, and frequent blood count monitoring, are in place to closely monitor for anemia.

For the R/R AML Mag+MEC cohort (Cohort 2), strong scientific and nonclinical data exist supporting the enhancement of efficacy when magrolimab is added to cytotoxic chemotherapy, including MEC. Furthermore, magrolimab is not anticipated to have overlapping hepatotoxicity.

For the Post-chemo Maint Mag+CC-486 cohort (Cohort 3), strong nonclinical and clinical data exist to support the rationale for combining magrolimab with CC-486. Given that CC-486 shares similar properties with azacitidine, it is anticipated that the combination of magrolimab with CC-486 will be as similarly well tolerated and effective as the combination of magrolimab with azacitidine. Magrolimab plus azacitidine has been well tolerated in AML patients to date, with no MTD reached and a 3.8% AE discontinuation rate in an ongoing study. A CR rate of 44% was observed with the combination, which is substantially higher than azacitidine monotherapy CR rates in historical studies. While CC-486 is not identical to the parenteral form of azacitidine, these agents have the same active substance and share many similarities. Therefore, CC-486 is anticipated to be well tolerated and effective when combined with magrolimab.

For all cohorts, specific safety assessments to monitor for expected toxicities to each of these agents will be implemented, including monitoring for anemia, myelosuppression, tumor lysis syndrome (TLS), hepatotoxicity, IRRs, and other expected toxicities.

During a pandemic, additional potential risks to patients have been identified and may include adequate study drug availability, interruptions to the study visit schedule, and adherence to protocol-specified safety monitoring or laboratory assessments. Refer to Appendix 3 for further details on the risks and risk mitigation strategy. Given the risk mitigation measures that are being implemented, the expected benefit-risk assessment to patients remains unchanged.

In summary, based on strong scientific rationale, nonclinical and emerging clinical efficacy data, and manageable safety profile with the proposed magrolimab combination regimens, this study has an acceptable risk:benefit ratio for patients who participate.

1.9. Compliance

This study will be conducted in compliance with this protocol, Good Clinical Practice (GCP), and all applicable regulatory requirements.

2. OBJECTIVES AND ENDPOINTS

Objectives and endpoints for Study GS-US-546-5920 are presented by cohort in Sections 2.1, 2.2, and 2.3. Analysis of the study endpoints is described in Sections 8.1.2, 8.1.3, and 8.1.4.

2.1. Safety Run-in Cohort 1 and Phase 2 Cohort 1 (1L Unfit AML Mag+Ven+Aza)

Primary, secondary, CCI objectives and endpoints for patients with newly diagnosed, previously untreated AML who are ineligible for intensive chemotherapy are as follows:

Primary Objectives	Primary Endpoints
 To evaluate the efficacy of magrolimab in combination with the anti-leukemia therapy venetoclax + azacitidine as determined by the CR rate (Phase 2 Cohort 1) To evaluate the safety and tolerability, and to determine the recommended Phase 2 dose (RP2D) of magrolimab in combination with the anti-leukemia therapy venetoclax + azacitidine (Safety Run-in Cohort 1) 	 CR rate, defined as the proportion of patients who achieve CR as determined by the investigator based on prespecified criteria (Phase 2 Cohort 1) Incidence of DLTs, treatment-emergent AEs, and laboratory abnormalities according to the National Cancer Institute (NCI) Common Terminology Criteria for Adverse Events (CTCAE) Version 5.0 (Safety Run-in Cohort 1)
Secondary Objectives	Secondary Endpoints
 To evaluate additional measures of efficacy of magrolimab in combination with the anti-leukemia therapy venetoclax + azacitidine To evaluate the safety and tolerability of magrolimab in combination with the anti-leukemia therapy venetoclax + azacitidine (Phase 2 Cohort 1) To evaluate the PK of magrolimab in combination with the anti-leukemia therapy venetoclax + azacitidine To evaluate the immunogenicity of magrolimab in combination with the anti-leukemia therapy venetoclax + azacitidine 	 ORR, including CR, CRi, CRh, partial remission (PR), and MLFS CR/CRi rate Complete remission without minimal residual disease (CR_{MRD}) rate Complete remission or complete remission with partial hematologic recovery (CR/CRh) rate Cytogenetic complete remission (cCR) Duration of responses (DOR) Duration of CR Duration of CR/CRi Duration of CR/CRh Event-free survival (EFS) OS RBC transfusion independence rate Incidence of treatment-emergent AEs and laboratory abnormalities according to the NCI CTCAE Version 5.0 (Phase 2 Cohort 1) Magrolimab concentrations over time Rate and magnitude of anti-magrolimab antibodies

2.2. Safety Run-in Cohort 2 and Phase 2 Cohort 2 (R/R AML Mag+MEC)

Primary, secondary, CCI objectives and endpoints for patients with R/R AML are as follows:

Primary Objectives	Primary Endpoints
To evaluate the efficacy of magrolimab in combination with the anti-leukemia therapy MEC as determined by the CR rate (Phase 2 Cohort 2)	CR rate, defined as the proportion of patients who achieve CR as determined by the investigator based on prespecified criteria (Phase 2 Cohort 2)
To evaluate the safety and tolerability, and to determine the RP2D of magrolimab in combination with the anti-leukemia therapy MEC (Safety Run-in Cohort 2)	Incidence of DLTs, treatment-emergent AEs, and laboratory abnormalities according to the NCI CTCAE Version 5.0 (Safety Run-in Cohort 2)
Secondary Objectives	Secondary Endpoints
To evaluate additional measures of efficacy of magrolimab in combination with the anti-leukemia therapy MEC	 ORR, including CR, CRi, CRh, PR, and MLFS CR/CRi rate CR_{MRD}-rate CR/CRh rate

- To evaluate the safety and tolerability of magrolimab in combination with the anti-leukemia therapy MEC (Phase 2 Cohort 2)
- To evaluate the PK of magrolimab in combination with the anti-leukemia therapy MEC
- To evaluate the immunogenicity of magrolimab in combination with the anti-leukemia therapy MEC
- cCR
- DOR
- Duration of CR
- Duration of CR/CRi
- Duration of CR/CRh
- EFS
- OS
- RBC transfusion independence rate
- Platelet transfusion independence rate
- Incidence of treatment-emergent AEs and laboratory abnormalities according to the NCI CTCAE Version 5.0 (Phase 2 Cohort 2)
- Magrolimab concentrations over time
- Rate and magnitude of anti-magrolimab antibodies

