3.1.1. Safety Run-in Cohorts

This study will include the following 3 safety run-in cohorts:

- Safety Run-in Cohort 1 (1L Unfit AML Mag+Ven+Aza), closed to enrollment globally as of Protocol Amendment 5: magrolimab + venetoclax + azacitidine in patients with newly diagnosed, previously untreated AML who are ineligible for intensive chemotherapy
- Safety Run-in Cohort 2 (R/R AML Mag+MEC): magrolimab + MEC in patients with R/R AML
- Safety Run-in Cohort 3 (Post-chemo Maint Mag+CC-486), closed to enrollment globally as of Protocol Amendment 5: magrolimab + CC-486 as maintenance therapy in patients with newly diagnosed AML who are in CR or CRi with MRD positivity following intensive chemotherapy

Initially, 6 patients will be enrolled into Safety Run-in Cohorts 1, 2, and 3 to receive study treatment according to the dose levels presented in Table 1, Table 2, or Table 3, respectively. A DLT assessment period of 1 cycle (28 days) will occur. The DLT assessment period and definition are provided in Sections 3.1.1.1 and 3.1.1.2.

Dose de-escalation decisions will be made as follows:

- If no more than 2 patients in a safety run-in cohort experience a DLT in Cycle 1, enrollment into the corresponding Phase 2 cohort will begin at this dose level.
- If 3 or more (> 33%) patients in a safety run-in cohort experience a DLT up to the end of Cycle 1, another 6 patients will be enrolled in that cohort at a lower dose and evaluated in the same manner to define the RP2D.

De-escalation dose levels for each safety run-in cohort are presented in Table 4, Table 5, and Table 6. Any dose de-escalation for Cohorts 1 and 3 will occur with the combination regimen, as there is a lack of dose-dependent toxicities observed with magrolimab in over 500 patients treated to date with magrolimab as monotherapy or in combination, and agents being evaluated in combination with magrolimab have identified or potential dose-related toxicities as cytotoxic agents (ie, venetoclax and CC-486). For Cohort 2, any dose de-escalation will occur with magrolimab, as the combination with chemotherapy (ie, MEC) has not been extensively studied. The selected RP2D for any cohort cannot exceed the identified MTD for that cohort.

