3.1.2. Phase 2 Cohorts

After completion of each safety run-in cohort and identification of the RP2D for that cohort, the corresponding Phase 2 cohort may be enrolled as follows:

- Phase 2 Cohort 1 (1L Unfit AML Mag+Ven+Aza), closed to enrollment globally as of *Protocol Amendment 5*: 40 patients with newly diagnosed, previously untreated AML who are ineligible for intensive chemotherapy will be enrolled to receive magrolimab + venetoclax + azacitidine
- **Phase 2 Cohort 2 (R/R AML Mag+MEC):** 30 patients with R/R AML will be enrolled to receive magrolimab + MEC.
- Phase 2 Cohort 3 (Post-chemo Maint Mag+CC-486), closed to enrollment globally as of *Protocol Amendment 5*: 40 patients with newly diagnosed AML who are in CR or CRi with MRD positivity following intensive chemotherapy may be enrolled to receive magrolimab + CC-486.

Up to 5 to 10 additional patients may be enrolled in each of the Phase 2 cohorts to collect additional safety, efficacy, and/or PK/PD data.

3.1.3. Closure of Cohorts 1 and 3

Cohort 1 closed to enrollment globally as of Protocol Amendment 5 and no new patients enrolled in Cohort 1 thereafter. A total of 18 patients were enrolled into Cohort 1 (7 patients in safety run-in and 11 patients in Phase 2).

Cohort 1 patients enrolled prior to sponsor's notification and implementation of Protocol Amendment 5 will continue on study, receive study treatment (Sections 3.3, 5.1, and 5.2), and undergo all study assessments (Section 6), until end of study or discontinuation criteria are met (Sections 3.4 and 3.5).

Cohort 3 closed to enrollment globally as of Protocol Amendment 5 and no patients were enrolled.

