4. PATIENT POPULATION

4.1. Number of Patients and Patient Selection

Up to approximately 164 patients will be enrolled in the study, with up to 54 patients in the safety run-in cohorts and up to 110 patients in the Phase 2 cohorts.

Refer to Section 3.1.3 for information on Cohort 1 patients enrolled prior to implementation of Protocol Amendment 5.

The following patient populations will be enrolled into the study:

- Safety Run-in Cohort 1 and Phase 2 Cohort 1 (1L Unfit AML Mag+Ven+Aza), closed to enrollment globally as of Protocol Amendment 5: patients with newly diagnosed, previously untreated AML confirmed based on World Health Organization (WHO) criteria who are age 75 years or older, or who are age 18 years to 74 years and have comorbidities that preclude the use of intensive chemotherapy
- Safety Run-in Cohort 2 and Phase 2 Cohort 2 (R/R AML Mag+MEC): patients with confirmation of AML by WHO criteria who are refractory to or have relapsed after the initial intensive chemotherapy
- Safety Run-in Cohort 3 and Phase 2 Cohort 3 (Post-chemo Maint Mag+CC-486), closed to enrollment globally as of Protocol Amendment 5: patients with confirmation of AML by WHO criteria who achieved CR or CRi with presence of MRD (MRD positive) after intensive induction chemotherapy with or without consolidation therapy prior to starting maintenance therapy

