8.1.2. Primary Endpoints

The primary endpoints for the Phase 2 cohorts are as follows:

- Rate of Complete Remission (Phase 2 Cohorts 1 and 2): The CR rate is defined as the proportion of patients who achieve CR (CR_{MRD} or complete remission with positive or unknown MRD [CR_{MRD}) as determined by the investigator based on prespecified criteria (Appendix 7) while on study prior to initiation of any new anti-AML therapy.
- Minimal Residual Disease Negative Complete Remission Rate (Phase 2 Cohort 3): The MRD negative CR rate is defined as the proportion of patients who maintain CR as determined by the investigator based on prespecified criteria (Appendix 7) and reach MRD negative disease status on 2 consecutive bone marrow assessments as determined using multiparameter flow cytometry with a sensitivity of < 0.1% while on study prior to initiation of any new anti-AML therapy. For this cohort, patients will need to have 2 consecutive MRD negative values to be considered MRD negative for analysis.

The primary endpoint for the safety run-in cohorts is as follows:

• Incidence of DLTs, as defined in Section 3.1.1.2, and incidence of treatment-emergent AEs and laboratory abnormalities according to the NCI CTCAE Version 5.0

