8.3. Analysis Conventions

8.3.1. Analysis Sets

8.3.1.1. Efficacy

The primary analysis set for efficacy analysis is the Full Analysis Set (FAS). The FAS includes all enrolled patients who receive at least 1 dose of any study treatment, with treatment group designated according to the assigned treatment.

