8.10. Sample Size

Sample size calculation is as follows:

 For Cohort 2, a sample size of 36 (30 patients in Phase 2 Cohort 2 together with 6 patients in Safety Run-in Cohort 2) provides an 83.1% power for a 1-group Chi-square test at 1-sided alpha of 0.1 level to detect a CR rate of ≥ 35% for the combination compared with a historical control CR rate of 19% {Greenberg 2004}.

The original protocol for the study included a Cohort 1, for which 46 patients were planned to be enrolled (6 patients in Safety Run-in and 40 patients in Phase 2); however, Cohort 1 was closed to enrollment following enrollment of 18 patients (7 patients in Safety Run-in and 11 patients in Phase 2).

The original protocol also included a Cohort 3, for which 46 patients were planned to be enrolled (6 patients in Safety Run-in and 40 patients in Phase 2); however, Cohort 3 was closed to enrollment and no patients were enrolled.

9. **RESPONSIBILITIES**

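### Cohort 2's primary CR test has no single population: the endpoint is labelled Phase 2 only (30 patients), the power counts 36, and the Full Analysis Set could take in more

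*Protocol*

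**What the plan says.** **Endpoint.** Section 2.2, and the synopsis with it, attaches the primary efficacy endpoint to one stage of the cohort: "CR rate, defined as the proportion of patients who achieve CR as determined by the investigator based on prespecified criteria (Phase 2 Cohort 2". Section 8.1.2 does the same under "Rate of Complete Remission (Phase 2 Cohorts 1 and 2" and gives the run-in cohorts a different primary endpoint (DLTs, adverse events and laboratory abnormalities). The secondary efficacy endpoints in Section 8.1.3 are headed by cohort, without the Phase 2 restriction.

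**Size.** Section 3.1.2 plans that "30 patients with R/R AML will be enrolled to receive magrolimab + MEC". Section 8.10 rests the power on "a sample size of 36 (30 patients in Phase 2 Cohort 2 together with 6 patients in Safety Run-in Cohort 2", with a CR rate of 35% against a historical 19%, a 1-group chi-square test at 1-sided alpha 0.1, and 83.1% power.

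**Analysis set.** Section 8.3.1.1: "The FAS includes all enrolled patients who receive at least 1 dose of any study treatment". Section 8.5.1 tests each cohort separately and sets no limit by stage, dose level or planned number.

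**Other patients who may be dosed in Cohort 2.**
- After 3 or more DLTs, "another 6 patients will be enrolled in that cohort at a lower dose and evaluated in the same manner to define the RP2D" (Section 3.1.1). Table 5 gives two lower levels.
- "Up to 5 to 10 additional patients may be enrolled in each of the Phase 2 cohorts" (Section 3.1.2), to add safety, efficacy or PK/PD data.
- Run-in patients not evaluable for DLT are replaced (Section 4.1.1). If they were dosed, they still meet the Full Analysis Set definition.

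**Total.** Section 4.1: "Up to approximately 164 patients will be enrolled in the study, with up to 54 patients in the safety run-in cohorts", plus up to 110 in Phase 2.

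**The concern.** Three parts of one document give three answers to the question of whose CRs are counted. The endpoint says Phase 2 patients. The sample size says Phase 2 plus six run-in patients. The analysis set says everyone dosed in the cohort. Cohort 2 is the only cohort still open and the only one with a power statement, so this is the trial's one powered efficacy test.

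Two things are at stake. The stated power does not belong to the endpoint as it is defined. And the rejection threshold depends on which population is used, so the same data could pass on one reading and fail on another. In an open-label trial with investigator-assessed response, that choice should be fixed before CRs are counted.

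**Working it through.** **Inputs** (Section 8.10): null rate p0 = 0.19, alternative p1 = 0.35, 1-sided alpha 0.1 (z = 1.2816), n = 36. Section 3.1.2: Phase 2 n = 30 and up to 10 add-ons. Section 3.1.1 and Table 5: 6 further patients per de-escalation and two lower levels, so up to 12 patients at levels not selected.

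**Formula** (normal approximation, null variance in the critical value):

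power = Φ{[(p1 − p0) − z·√(p0(1 − p0)/n)] / √(p1(1 − p1)/n)}

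**Plan's own figure, n = 36.** √(0.1539/36) = 0.0654 and √(0.2275/36) = 0.0795. Then (0.16 − 1.2816 × 0.0654)/0.0795 = 0.959, and Φ = 0.831. The stated 83.1% reproduces.

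**Endpoint as labelled, n = 30.** √(0.1539/30) = 0.0716 and √(0.2275/30) = 0.0871. Then (0.16 − 1.2816 × 0.0716)/0.0871 = 0.783, and Φ = 0.783. Power is 78.3%, which is 4.8 points lower.

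**CRs needed to reject.** This is the smallest whole number above n·p0 + z·√(n·p0(1 − p0)).

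| Population | n | Threshold | CRs needed | Power by formula |
|---|---|---|---|---|
| Phase 2 only | 30 | 8.45 | 9 | 78.3% |
| Phase 2 + 6 run-in at the RP2D | 36 | 9.86 | 10 | 83.1% |
| The 36 + 10 add-ons | 46 | 12.15 | 13 | 88.9% |
| The 36 + 12 at levels not selected | 48 | 12.60 | 13 | 89.8% |

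The last two rows assume that every patient has a true CR rate of 35%.

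**Patients at levels not selected.** The protocol gives no CR rate for them, so the effect has to be shown as a range. Take 36 patients at 35% and 12 at an assumed rate, and add the two binomial distributions. The exact probability of at least 13 CRs in 48 is:
- 77.1% if the 12 respond at 19%
- 83.1% if they respond at 25%
- 90.6% if they respond at 35%

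**Enrolment total.** 164 = 54 + 110, and 110 = 40 + 30 + 40, so the add-ons are not in it. It still counts Cohort 1 and Cohort 3 in full, although Section 3.1.3 says they closed with 18 and 0 patients.

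**The case against.** The best defence is that the operative analysis text mostly agrees. The Full Analysis Set is all dosed patients, the test is by cohort, and Section 8.10 says 30 + 6. On that reading pooling was intended and only the stage label in Sections 2.2 and 8.1.2 and the synopsis is out of line. The Full Analysis Set also groups patients by assigned treatment, which could be read as separating dose levels, and a SAP might settle the rest.

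Part of this stands. Pooling 30 + 6 probably was the intention, and 83.1% is right for it. But the label and the sample-size basis are both fixed in the protocol, so a SAP that follows one contradicts the other. Nothing says that assigned treatment means dose level, and pooling by cohort leaves add-on patients inside the test.

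A reader might infer more than the text supports:

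- *That patients at levels not selected dilute the result.* De-escalation in Cohort 2 lowers magrolimab and leaves MEC unchanged, so these patients would have received more magrolimab than the RP2D. No passage supports giving them only the historical rate. They exist only if de-escalation occurs.
- *That add-ons inflate type I error.* Testing at 36 and again at 46 would raise the chi-square rule's error from 13.1% to 14.6%, and testing after every added patient would give 17.5%. The protocol schedules neither. Section 8.2.2 plans one primary analysis, and Section 3.1.2 ties the add-ons to no response result. The 13.1% comes from the discreteness of the chi-square rule at n = 36, whatever the population. A single test at n = 46 has a true size of 8.3%.
- *That power at n = 30 is 64%.* That figure belongs to an exact test (at least 10 of 30) that is not planned. Its counterpart at n = 36 is 76.6%, not 83.1%.

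**Conclusion.** The point holds as an internal contradiction. The primary endpoint covers 30 patients, the power covers 36, and the analysis set has no limit by stage, dose level or add-on status. The conflict between 30 and 36 depends on no contingency. By the protocol's own formula it is worth 4.8 points of power (83.1% against 78.3%) and moves the threshold from 9 of 30 to 10 of 36.

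The wider populations are conditional: patients at other levels on de-escalation, and add-ons on the option being used. Their effect on power has no fixed direction. At n = 48 it runs from about 77% to about 91% as the assumed CR rate goes from 19% to 35%. The power calculation itself contains no error, and the protocol plans no repeated testing.

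The 164 total is a minor point. It is worded as an approximate ceiling, and the closures are stated elsewhere.

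**What to change.** In the synopsis and Sections 2.2, 8.1.2, 8.3.1.1 and 8.5.1, name one primary efficacy set for Cohort 2 that agrees with Section 8.10: all dosed run-in and Phase 2 patients assigned to the RP2D. That is 30 + 6 planned, plus any dosed run-in patient at that level who was replaced. Because Section 3.3 lets run-in patients switch to the RP2D later, say that the assignment at entry counts.

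Run the hypothesis test once on that set, at the primary analysis. Report run-in patients at other dose levels and any add-on patients descriptively and in a sensitivity analysis.

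If the Phase 2-only label is kept instead, change Section 8.10 and the synopsis to 78.3% power at n = 30.

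As a minor edit, update the 164 in the synopsis and Section 4.1 for the closed cohorts, the add-ons and replacements. A hard cap built from planned run-in sizes would be unsafe: replacement is open-ended, and Cohort 1's run-in already enrolled 7 rather than 6.

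The cost is wording in the protocol, carried into the SAP. The downside is that add-on patients do not contribute to the formal test.
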